8.2 Endpoints

8.2.1 Primary endpoints

The six month post-activation visit serves as the primary endpoint for data collection related to efficacy and safety outcomes post-CI532 implantation:

1. Efficacy endpoints

- 1.1. Hearing in the implanted ear will be reported as the change in pure-tone air-conduction thresholds (dB HL) pre-operatively to post-activation according to the Cochlear consensus at six months post-activation and 12 months post-activation.

Audiometric data will be summarized at each follow-up time point to assess any changes in hearing sensitivity and to characterize the impact of the procedure on hearing.

To understand if measurable low frequency thresholds can be maintained with implantation using the CI532 cochlear implant and fit with the acoustic component

- 1.2. Assessment of speech recognition in quiet will be measured using the CNC monosyllabic word test (7). Assessment of speech recognition in noise will be measured using sentences drawn from the Australian Sentence In Noise (AuSTIN) test (8) with speech-weighted noise (SWN) at a fixed +5 dB SNR.

2. Safety endpoints

- 2.1. Adverse events will be summarized by event type, severity, seriousness, as well as relatedness to the device and implant procedure will be reported and tabulated.

- 2.2. Report of medical/surgical and device related adverse events compared to the current approved labelling with regard to type, frequency and seriousness.

8.2.2 Secondary endpoints

The six month post-activation visit serves as the secondary endpoint for data collection related to Patient Reported Outcomes (PRO):

1. Speech, Spatial and Qualities of Hearing scale (SSQ)

The six month post-activation visit serves as the secondary endpoint for data collection related to self-reported auditory disability and quality assessment with the SSQ for the CI532 cochlear implant.

2. Glasgow Benefit Inventory

The six month post-activation visit serves as the secondary endpoint related to health utility data collection with the GBI for the CI532 cochlear implant.

8.3 Additional clinical measures

8.3.1 Device characteristics

Report of device characteristics related to impedance, psychophysical T and C-levels and ECAP with the CI532 cochlear implant.

8.3.2 Electrode placement

Report of EA32 electrode placement as confirmed by X-ray (preferably a lateral or modified Stenver's view).

8.3.3 Surgical questionnaire

Report on the usability and surgical outcomes with the CI532 cochlear implant as obtained via surgical questionnaire.

8.4 Equipment

Speech perception performance in quiet will be assessed using a loud speaker configuration with the signal from the front (S0). Speech perception performance in noise will be assessed using a loud speaker configuration with signal from the front and noise from the implanted side (S0N90 or S0N270) as shown in Figure 2.

Figure 2: Speaker orientation for speech perception assessment

The loudspeakers are located at head height for a seated subject (reference point). The distance from the loudspeaker from the reference point is approximately one meter. There will be defined locations for the loudspeakers and subject within the test environment. Sound field calibration of the Average Sound Level (Leq) is performed prior to each visit using a sound level meter (SLM) using a dB A-weighting (dBA), slow time weighting. Calibration of the SLM will occur according to the centres' current practise.

8.5 Investigation schedule

The visit dates and measures to be applied are reported in the Investigation schedule in Table 1.

8.6 Subjects

8.6.1 Inclusion Criteria

1. Meet current cochlear implant indications at the implanting centre
2. In addition to meeting current cochlear implant indications, subjects must also possess preoperative unaided hearing thresholds between 40 to 65 dB HL at 250 & 500Hz in the ear to be implanted⁴
3. Fluent⁵ speaker in the local language used to assess clinical performance

⁴ If it is more than 90 days past the date of the Candidacy Evaluation, candidacy needs to be reconfirmed by repeating hearing threshold test measures at 250 and 500Hz. Any changes observed will need to be reviewed in consultation with the Sponsor prior to surgery occurring.

4. Eighteen years of age or older at the time of implantation with no upper age limit

8.6.2 Exclusion Criteria

1. Evidence of hearing loss prior to 5 years of age.
2. Sensorineural severe-to-profound hearing loss greater than 20 years at 2 kHz and above
3. Simultaneous bilateral cochlear implantation or prior cochlear implantation in the ear to be implanted.
4. Additional disabilities that may affect the subject's participation or safety during the clinical investigation.
5. Medical or psychological conditions that contraindicate undergoing general anaesthesia or surgery.
6. Ossification, malformation or any other cochlear anomaly, such as common cavity, that might prevent complete insertion of the electrode array, as confirmed by medical examination.
7. Hearing impairment due to lesion or neuropathy of the acoustic nerve, VIII nerve or central auditory pathway.
8. Active middle-ear infection,
9. Tympanic membrane perforation
10. Unrealistic expectations on the part of the subject, regarding the possible benefits, risks, and limitations that are inherent to the surgical procedure(s) and prosthetic devices
11. Unwillingness or inability of the candidate to comply with all investigational requirements.
12. Patients with existing CSF shunts or drains, existing perilymph fistula, skull fracture or CSF leak.
13. Patients with recurrent episodes of bacterial meningitis

8.6.3 Number of subjects required

The protocol describes a feasibility study within a single site and a limited number of subjects (12 subjects) to characterise the audiological outcomes and the feasibility of fitting of the acoustic component postoperatively associated with the CI532 cochlear implant in adult cochlear implant candidates. As such, there have been no power or sample size estimations performed. It is estimated to take six months to recruit this number of subjects. The enrolment period will be extended if required.

⁵ As judged by the investigator i.e. able to complete the speech perception assessment tasks and questionnaires.

8.6.4 Criteria and procedures for subject's withdrawal or discontinuation

Any subject may voluntarily discontinue the study at any time without prejudice. The Investigator may discontinue a subject from the study at any time if (s)he considers that remaining in the study compromises the subject's health or the subject is not sufficiently cooperative. In either event, reason(s) for discontinuation should be recorded on a study withdrawal form, provided as part of the CRFs for the study. Possible reasons for study discontinuation include the following:

- AE necessitating discontinuation from the study
- The subject is lost to follow-up
- Voluntary decision to withdraw consent made by the subject⁶
- Investigator decision⁷
- Other reason

In case of a subject lost-to-follow-up, the Investigator must attempt to contact the subject (or relative/family contact) by phone, email or letter at least three times. If attempts are unsuccessful, the 'subject withdrawal' form is to be completed in the study file and reported, as appropriate, in required reports to the Sponsor, EC and TGA.

During surgery, an alternative device (e.g., CI522 or CI512) may be implanted in subjects where there are substantial difficulties with the CI532. These subjects will continue the clinical investigation and their outcomes will be compared to those subjects who received the CI532 device.

8.6.5 Subject replacement

The total number of subjects enrolled in the clinical investigation is 12. If a subject withdraws pre-operatively, they will be replaced by a newly recruited subject who meets the selection criteria for participation.

8.6.6 Point of enrolment

Subjects are recruited to the study by the investigators usually during the course of medical consultation. Subjects will be sequentially enrolled once Cochlear Asia Pacific receives a properly executed Informed Consent form and has approved the preoperative candidacy evaluation in writing.

⁶ Withdrawal of consent is defined as the subject's voluntary decision to revoke consent to continue participation in the study.

⁷ Subject withdrawal from the study is defined as an Investigator decision. The Investigator may elect to withdraw a subject from the study at any time if he/she considers that remaining in the study compromises the patient's health or if the Investigator considers the subject lost to follow-up.

8.6.7 Total expected duration of the clinical investigation

The total expected duration of the clinical investigation is 38 months. The total duration will be dependent on the ability to recruit the required number of subjects within the enrolment period.

8.7 Procedures

8.7.1 Medical history (Pre-op)

Information regarding subject hearing-history (e.g., etiology, onset of hearing loss, duration of severe-to-profound hearing loss, amplification use) will be obtained and reported on the respective case-report form. In addition, patients will be carefully and extensively counseled to ensure that their expectations from cochlear implantation are reasonable and appropriate (as determined by the Investigator).

8.7.2 Audiogram (Candidacy, Activation, 3 months, 6 months and 12 months post-activation)

An unaided audiogram will be performed for both ears⁸ at candidacy⁹, at initial activation, three, six and 12 months post-activation at the following pure-tone frequencies:

Air conduction: 125, 250, 500, 750, 1000, 1500, 2000, 3000, 4000, 6000 & 8000 Hz

Air conduction thresholds >80 dB HL at 125 Hz, >90 dB HL at 250 Hz, >100 dB at 8000 Hz and >120 dB for other test frequencies will be marked NR (no response).

Bone conduction: 125¹⁰, 250, 500, 750, 1000, 1500, 2000, 3000, 4000 Hz

Bone conduction thresholds >20 dB HL at 125 Hz, >30 dB HL at 250 Hz, >60 dB HL at 500 Hz and >70 dB HL for other test frequencies will be marked NR (no response).

Where the recipient reports feeling rather than hearing the acoustic stimuli, the threshold shall be recorded as vibrotactile (VT).

An aided audiogram will be performed for both ears at candidacy, and the implanted ear at initial activation¹¹, three, six and 12 months post-activation at the following frequencies using warble tones:

Aided thresholds: 125, 250, 500, 750, 1000, 1500, 2000, 3000, 4000 Hz

Tympanometry in each ear at each visit.

⁸ The use of tube phones and appropriate masking of the non-test ear is required.

⁹ If it is more than 90 days past the date of the Candidacy Evaluation, candidacy needs to be reconfirmed by repeating the air conduction hearing threshold test measure at 250 and 500Hz. Any changes observed will need to be reviewed in consultation with the Sponsor prior to surgery occurring.

¹⁰ Bone conduction measures at 125 Hz are optional based on potential audiometric equipment limitations.

¹¹ Assessing aided thresholds after the initial activation will only be conducted if there is a shift in unaided hearing of more than 10 dB HL (for the better or worse) at two or more aidable frequencies.

8.7.2.1 Determination of hearing preservation post CI532 implantation

Unaided air conduction (AC) hearing thresholds will be reported for all participants at six months and twelve months post-activation to support the primary efficacy endpoint.

The population implanted with the CI532 device (per protocol population) will be divided into two groups for analysis:

1. Participants with a total hearing loss (no measureable AC threshold at audiometer limits at each frequency)
2. Participants with preserved hearing (measureable AC threshold at 250, 500 and 750 Hz)

Hearing preservation post CI532 implantation will be considered to be functional hearing preservation as defined by the Cochlear consensus¹²:

- i. Unaided AC hearing thresholds ≤ 70 dB HL at 250 Hz
- ii. Unaided AC hearing thresholds ≤ 90 dB HL at 500 Hz
- iii. Unaided AC hearing thresholds ≤ 90 dB HL at 750 Hz

The number of participants with a total hearing loss, preserved hearing and preserved functional hearing post CI532 implantation will be reported for each frequency (250, 500 & 750 Hz¹³).

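### The functional-preservation limit at 750 Hz ignores baseline, and entry does not control 750 Hz, so an ear already above 90 dB HL there cannot count as functional at 750 Hz even if it loses nothing

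*Combined protocol and SAP*

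**What the plan says.** **Entry.** Inclusion criterion 2 (section 8.6.1, repeated in the synopsis) is that "subjects must also possess preoperative unaided hearing thresholds between 40 to 65 dB HL at 250 & 500Hz in the ear to be implanted". If more than 90 days pass after the candidacy evaluation, section 8.7.2 reconfirms candidacy by "repeating the air conduction hearing threshold test measure at 250 and 500Hz". The only criterion in 8.6.2 that names higher frequencies is exclusion 2: "Sensorineural severe-to-profound hearing loss greater than 20 years at 2 kHz and above". It concerns how long a loss has lasted and sets no level at 750 Hz.

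**Measurement.** The candidacy audiogram does include 750 Hz: "Air conduction: 125, 250, 500, 750, 1000, 1500, 2000, 3000, 4000, 6000 & 8000 Hz". For 750 Hz, the no-response rule in the same section is ">120 dB for other test frequencies will be marked NR (no response".

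**Classification.** Section 8.7.2.1 has two tiers.
- The first divides CI532 recipients into total loss (no measurable threshold at any of the frequencies) and "Participants with preserved hearing (measureable AC threshold at 250, 500 and 750 Hz".
- The second equates hearing preservation with functional preservation under the sponsor's consensus: at most 70 dB HL at 250 Hz, at most 90 dB HL at 500 Hz, and "Unaided AC hearing thresholds ≤ 90 dB HL at 750 Hz".

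Neither tier mentions the pre-operative threshold. The section closes by saying that the numbers in each category are reported by frequency (250, 500 and 750 Hz).

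**Alongside.** Efficacy endpoint 1.1 in section 8.2.1 reports the pre- to post-operative change in thresholds. Section 9 adds individual-level proportions of subjects who are better, unchanged or worse on audiometry.

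**The concern.** A count labelled as preservation should separate hearing lost after implantation from hearing that was absent beforehand. At 250 and 500 Hz the entry criterion does this, because every eligible ear starts inside the functional limit. At 750 Hz nothing does. An ear that enters above 90 dB HL and does not change is recorded as not functional at 750 Hz, exactly as an ear that surgery pushed over the limit would be.

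Section 3 says the inclusion criteria were built to demonstrate that the electrode and its insertion are atraumatic. It adds that the results may feed into a later randomised study of functional hearing preservation. Section 8.7.2.1 is the only place where that quantity is defined. If the 750 Hz or joint count is read as the effect of insertion, pre-existing loss makes the device look worse, by an amount that depends on the audiogram slopes of the subjects who happen to enrol.

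**Working it through.** The plan gives no power or sample-size calculation (section 8.6.3), so there is no stated figure to reproduce. The check applies the plan's own rules to an ear that does not change.

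**Inputs**
- Entry range: 40 to 65 dB HL at 250 and 500 Hz; none at 750 Hz (8.6.1).
- No response: above 90 dB HL at 250 Hz; above 120 dB at 500 and 750 Hz (8.7.2).
- Functional limits: 70, 90 and 90 dB HL at 250, 500 and 750 Hz (8.7.2.1).
- Sample size: 12 (8.6.3). All 12 are taken to receive the CI532.

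**Step 1. Room between entry and the functional limit** (limit minus entry threshold)
- 250 Hz: 70 − 65 = 5 dB to 70 − 40 = 30 dB.
- 500 Hz: 90 − 65 = 25 dB to 90 − 40 = 50 dB.
- 750 Hz: not bounded by entry. It is negative for any ear that starts above 90 dB HL, for example 90 − 95 = −5 dB.

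**Step 2. Classification with zero shift**, 65 dB HL at 250 and 500 Hz before and after

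| 750 Hz, before and after | Preserved-hearing group | Total-loss group | Functional at 250 / 500 | Functional at 750 | Functional jointly |
|---|---|---|---|---|---|
| 90 dB or better | yes | no | yes / yes | yes | yes |
| 95 to 120 dB | yes | no | yes / yes | no | no |
| No response (above 120 dB) | no | no | yes / yes | no | no |

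The middle row is the main point. The bottom row is a second gap with the same cause: that subject belongs to neither group.

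**Step 3. Effect on the count.** If k of 12 subjects enter above 90 dB HL at 750 Hz and no ear changes, the highest attainable 750 Hz or joint functional rate is (12 − k)/12. The intervals are exact (Clopper-Pearson).

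| k (assumed) | Ceiling | 95% interval |
|---|---|---|
| 0 | 12/12 = 100% | 73.5 to 100% |
| 1 | 11/12 = 91.7% | 61.5 to 99.8% |
| 2 | 10/12 = 83.3% | 51.6 to 97.9% |
| 3 | 9/12 = 75.0% | 42.8 to 94.5% |

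With an at-risk denominator the same data give (12 − k)/(12 − k) = 100% in every row.

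**Step 4. How likely is k ≥ 1?** The documents give no distribution of 750 Hz thresholds, so the share p of eligible subjects above 90 dB HL is an assumption. P(k ≥ 1) = 1 − (1 − p)^12:
- p = 2%: 22%
- p = 5%: 46%
- p = 10%: 72%
- p = 20%: 93%

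**Step 5. Slope required.** The interval from 500 to 750 Hz is log2(750/500) = 0.58 octave. Starting from 65 dB HL at 500 Hz, the threshold must worsen by more than 25 dB over that interval to exceed 90 dB HL; starting from 40 dB HL, by more than 50 dB. The criteria permit such audiograms, but they are steep.

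**The case against.** The strongest reply has four parts.

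1. **Change from baseline is already reported.** Endpoint 1.1 would show zero shift for such an ear, and the individual analysis in section 9 would call it unchanged. This stands, and it limits the harm: the artefact can be recognised from data the plan collects. It does not remove it, because 8.7.2.1 would count the same ear as not functionally preserved, and no rule links the two results.

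2. **An absolute limit can be intended.** The study also asks whether the acoustic component can be fitted (sections 6 and 8.6.3), and for that question post-operative status matters whatever its cause. The consensus behind the limits is not reproduced in the plan and may deal with baseline. This is a good reason to keep the cut-offs and the all-subjects count. It does not justify calling an unchanged ear unpreserved without showing where it started.

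3. **Reporting is by frequency.** This stands. The 250 and 500 Hz rows are untouched. The ceilings in step 3 apply only to the 750 Hz row, or to a joint count if one is made, which the text leaves open.

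4. **Nothing is tested on this count.** Section 5.2 states no formal hypothesis and section 9 sets no pass/fail criterion. This also stands: a descriptive count is distorted, not an error rate.

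A reader might infer more than the documents support:
- That an ear above 90 dB HL at 750 Hz also drops out of the preserved-hearing group. It does not: that group needs only a measurable threshold, which at 750 Hz extends to 120 dB.
- That exclusion 2 shows such steep losses are expected. It limits duration at 2 kHz and above and is silent on 750 Hz.
- That a later randomised trial would necessarily inherit a wrong rate. Section 3 says only that the results may support its development.

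**Conclusion.** The point holds in a limited form. The functional limit at 750 Hz takes no account of baseline and entry does not control that frequency, so pre-existing loss can be counted as failure to preserve in the 750 Hz row and in any joint count. Each affected subject costs 8.3 points out of 12. A subject with no response at 750 Hz before surgery also falls outside both groups in 8.7.2.1.

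That the rule behaves this way follows from the text alone. The size of the effect rests on two assumptions: that all 12 subjects receive the CI532, and that some number k enter above 90 dB HL at 750 Hz. The documents do not indicate k, and it may be zero. The case for changing the plan is that the correction is cheap and uses data already collected, not that a large bias has been shown.

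**What to change.** In section 8.7.2.1:

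1. At each of 250, 500 and 750 Hz, report the functional count among subjects who met that frequency's functional limit at the pre-operative audiogram. Report the measurable count among those with a measurable threshold there. Show the number at risk as the denominator.
2. Give the all-subjects count beside each, so that post-operative status for acoustic fitting stays visible.
3. List separately the subjects who were already above 90 dB HL at 750 Hz before surgery, marking any with no response, and give their pre- and post-operative thresholds. This also covers subjects who fit neither group.
4. State whether the three functional limits are applied per frequency, jointly, or both.

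Eligibility, the consensus cut-offs and the test schedule do not change, and the 750 Hz candidacy threshold is already in the audiogram required by 8.7.2. The cost is a few sentences and an extra column. The drawback is that the 750 Hz denominator may fall below 12, which makes an already imprecise proportion less precise. At 250 and 500 Hz the entry criterion places every eligible subject inside the limits, so those denominators should not shrink on this account.

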8.7.3 Speech recognition (Candidacy, 3, 6 and 12 months post-activation)

Speech recognition will be measured pre-operatively, 3, 6, 12 months post activation. Pre-operatively, speech recognition will be evaluated in the unilateral aided condition with the contralateral ear masked or plugged. Post-activation, the best unilateral listening condition will be evaluated; "Implant ear" using the acoustic component and/or the CI SP alone on one ear with the contra-lateral ear plugged or masked. Post-activation speech recognition shall be evaluated with default Nucleus 6 input processing options (SCAN).

Assessment of speech perception in quiet will be measured using two lists of CNC monosyllabic word test (7) at 60 dBA in the S0 speaker orientation (Figure 1).

Assessment of speech understanding in noise will be measured using two lists drawn from the AuSTIN test (8) sentence lists spoken by a female talker at 60 dBA at a fixed +5 dB signal-to-noise ratio (SNR) in the S0N90 or S0N270 speaker orientation (Figure 1). The competing noise will be speech-weighted noise (SWN).

No lists will be repeated for a given subject during the clinical investigation.

Performance benefits are change in scores pre- to post-operatively:

1. Gain in speech recognition in quiet (% correct)

¹² Cochlear clinical consensus for determination of residual hearing preservation (05/11/2015)

¹³ The mean or median as statistically appropriate based on distribution of data.

2. Gain in speech recognition in noise (% correct)

8.7.4 Speech, Spatial, Qualities of Hearing scale – SSQ (Candidacy, 6 months post-activation)

Subjective quality assessment will be measured using the SSQ preoperatively and again at 6 months post-activation. The questionnaire will be completed during the visit by interview of the subject with the investigator.

Subjective performance benefits are change in scores pre- to post-operatively:

1. Gain in SSQ score (-10 to +10)

8.7.5 Glasgow Benefit Inventory – GBI (6 months post-activation)

Health Utility assessment will be measured using the GBI at six months post-activation. The questionnaire will be completed during the visit by interview of the subject with the investigator.

Subjective performance benefits are change in scores pre- to post-operatively:

1. GBI score (-100 to +100)

8.7.6 Video (Surgery)

Surgery may be recorded via a video camera connected to the surgeon's microscope.

